4. STUDY DESIGN AND METHODS

a. Study overview

Although most of our prior targets were primarily, if not exclusively, expressed in brain, COX-1 and COX-2 are present in the entire body and play important roles in the periphery: physiology, pathophysiology, and drug treatment. In fact, our prior studies in monkeys demonstrated that COX-1 is expressed at much higher densities in some peripheral organs (e.g., spleen, GI tract, and kidney) than in brain. For this reason, the phases of evaluating this COX-2 radioligand differ from those for brain-dedicated radioligands. That is, we normally do dedicated brain kinetic imaging before whole body imaging. For this target, by whole-body imaging in patients with RA and IIM, we wish to determine whether the radioligand actually labels COX-2 (based on blocking studies using a selective COX-2 inhibitor), and whether the most robust signal for COX-2 is in the peripheral inflammatory focus by whole-body imaging.

This is a multi-site center study in three groups of participants: patients with RA, patients with IIM, patients with AxSpA, and healthy volunteers as a control group. As noted above, participants must meet inclusion and exclusion criteria and sign an informed consent document. This study consists of four phases: 1) initial $[^{11}\text{C}]$ MC1 whole-body imaging of two single healthy volunteers with a low injection activity; 2) $[^{11}\text{C}]$ MC1 whole-body imaging in baseline and pre-blocked condition with a COX-2 selective antagonist (celecoxib). 3) Dedicated brain imaging using $[^{11}\text{C}]$ MC1, concurrent arterial blood sampling, in RA patients compared to healthy volunteers. 4) $[^{11}\text{C}]$ MC1 whole-body imaging of RA patients at baseline and after clinically indicated therapy.

To estimate the radiation exposure from the new radioligand $[^{11}\text{C}]$ MC1, we will follow the prior suggestions from our laboratory (Zanotti-Fregonara and Innis, 2012), which have been approved by the NIH Radiation Safety Committee. Specifically, we found that the average exposure of all published human studies with ^{11}C -radioligands more accurately reflected the exposure to humans than estimation based on imaging in monkeys with that particular radioligand.

Phase 1: We will do whole-body scanning in one male and one female healthy volunteer with $[^{11}\text{C}]$ MC1 using up to 10 mCi. We will measure uptake in the ovaries and testes and calculate the dose of radioactivity. Phase 2 will be proceeded only if the dose to these organs from the higher injected activity proposed in Phase 2 will not exceed the limits specified by the Radioactive Drug Research Committee (RDRC). If the dose of radioactivity already exceeds the RDRC limitation in the first participant of Phase 1, IRB will be consulted before the second participant of Phase 2 undergoes $[^{11}\text{C}]$ MC1 PET scan.

Phase 2: Fifteen patients with RA, fifteen patients with IIM, and fifteen healthy volunteers will have two whole-body PET/CT scans using 15 mCi of $[^{11}\text{C}]$ MC1. Fifteen patients with AxSpA will undergo two whole-body PET/MRI scans using 15 mCi of $[^{11}\text{C}]$ MC1. The first scan will serve as the baseline for comparison to pre-blocked scan and will provide dosimetry information, and the second scan will be a pre-blocking study using the COX-2 selective antagonist celecoxib. Two scans are necessary because the specific binding can only be estimated by comparing a scan at baseline and a scan after blockade.

Phase 3: Twelve RA patients and twenty-two healthy volunteers will have dedicated brain imaging with 20 mCi of $[^{11}\text{C}]$ MC1 at baseline and after blockade by celecoxib.

Phase 4: Fifteen RA patients will have a whole-body scan with 15 mCi of $[^{11}\text{C}]$ MC1 at baseline and after two to four months of clinically indicated therapy. The repeat scan will be initiated if the RA participant has substantial improvement of symptoms or by four months, whichever occurs first.

NOTE: A subject may participate in only one phase of the study.

We will proceed in the order of Phase 1 and 2. In Phase 2, all three groups of participants will be recruited and scanned randomly without specific order. Each PET scan will take up to two hours. Two PET scans on a day will be separated by at least 2.5 hours to allow for decay of the first injection ($T_{1/2} = 20$ min). In IIM patients, for the purpose of localizing inflammatory

focus in muscle, a whole-body MRI will be obtained before or after the PET scan and can be performed on the same day depending on the schedule of the radiology and PET departments. The completion of MRI will take approximately one hour. For AxSpA patients, a whole body PET/MRI will be obtained meaning that MRI imaging will be done simultaneously with the PET scan. MRI is not obtained in RA patients since the inflamed joints are generally well-identified by other clinical parameters.

Number of visits and time commitment of participants

Phase 1: whole-body imaging with 10 mCi [¹¹C]MC1 injection

1st outpatient visit: pregnancy test; whole body PET (4 hours)

Phase 2: whole-body imaging with 15 mCi [¹¹C]MC1 at baseline and after celecoxib

1st outpatient visit (only for patients with RA, AxSpA or IIM): clinical evaluations and screening procedures;

2nd outpatient visit (all participants): pregnancy test; baseline & blocked whole body PET/CT imaging (8 hours). For AxSpA patients, this will be PET/MRI (8 hours) instead of PET/CT.

3rd or 4th outpatient visit (only for patients with IIM): pregnancy test; whole-body MRI (2 hours)

Phase 3: brain-dedicated imaging with 20 mCi [¹¹C]MC1 at baseline and after celecoxib

1st outpatient visit: clinical evaluations and screening procedures

2nd or 3rd outpatient visit: pregnancy test; baseline & blocked [¹¹C]MC1 PET imaging (8 hours)

2nd or 3rd outpatient visit: pregnancy test; brain MRI (2 hours)

Phase 4: whole-body imaging with 15 mCi [¹¹C]MC1 at baseline and after two to four months of therapy

1st outpatient visit (only for patients with RA): clinical evaluations and screening procedures

2nd outpatient visit: pregnancy test; baseline whole body PET imaging (4 hours)

3rd outpatient visit: pregnancy test; post-therapy whole body PET imaging (4 hours)

All procedures and their associated exposure to radiation are for research purposes only. Each subject will not participate in more than one phase of this study.

b. Recruitment

Patients with RA, AxSpA or IIM will be recruited by advertisements */IRB-approval for which will be obtained based on the requirements in OHSRP Policy 302* (“Subject Recruitment and Compensation”) placed in medical journals, on websites/email list-servers of medical professionals, in patient support group or registry mailings, and/or in a variety of patient support group literature and websites, including new patient communication sites, such as Facebook, MySpace, Twitter, and Google Adwords for distribution as allowed by NIH policies as needed to reach the target enrollment numbers. AxSpA patients may also be referred from NIAMS protocol 11AR0223 (Studies on the Natural History and Pathogenesis of Spondylarthritis).

Healthy volunteers will be recruited under protocol 01M0254 “The Evaluation of Participants with Mood and Anxiety Disorders and Healthy Volunteers” or 17M0181,

“Recruitment and Characterization of Healthy Research Volunteers for NIMH Intramural Studies”.

Flyers (with tear offs) may be posted on NIH bulletin boards, at coffee shops, grocery stores, community centers, bookstores, NIH Clinical Center, libraries or placed in doctor’s office waiting rooms, retail establishments as well as on public transportation vehicles and/or bus shelters/train stations may be used (all with permission and according to the guidelines of the facility) or sent electronically (without tear offs) to those who request a copy.

Recruitment for Healthy volunteers will also include use of Research Match, Listservs, Craig’s List, advocacy websites, resource listings or other website postings and Study-specific page on the NIMH-IRP: Join A Study Website with URL (placeholder). Short text descriptions of this study will also appear on Facebook. Facebook posts will be made only via official NIMH accounts. Associate Investigators and members of the NIMH Marketing & Community Relations Unit will distribute recruitment materials.

All recruitment materials, including listserv notices, social media, letters to physicians, recruitment website content, and other venues will be approved by the IRB prior to use.

NIH Employees/staff will not be directly recruited by or through their supervisors or co-workers to participate in this study.

c. Screening

Patients with RA, AxSpA or IIM will be screened under this protocol. The screening process for AxSpA and IIM patients will additionally ensure that there are no contraindications to MRI. Basic screening may include physical exam, medical history, questionnaires, and laboratory tests: hematology (CBC with differential); chemistry (electrolytes, LFT’s, glucose, BUN, creatinine, Ca, Mg, phosphorus, uric acid, transaminases, total protein, albumin, CK, LDH, alkaline phosphatase); urinalysis; urine pregnancy test (females); acute phase reactants (ESR, CRP); serology (RF, ANA, immunoglobulins, anti-cardiolipin (ACA), anti-dsDNA, ANCA); anti-CCP antibodies and, if clinically indicated, spot urine protein to creatinine ratio. In addition, myositis associated or myositis specific antibodies will be obtained, if clinically indicated. HIV screening test; hepatitis panel (A, B, C); Tb test; others as required. X-ray, CT or MRI of clinically involved area will be obtained if clinically indicated. Additional studies on selected subjects, when indicated for diagnosis, will include: muscle biopsy or synovial biopsies with a separate informed consent; electromyography (EMG); swallowing tests; and others. Screening results will be reviewed by a clinically credentialed investigator before the subject undergoes any specific study procedures. No subjects will be withdrawn from NSAIDs including aspirin or corticosteroids exclusively for the purpose of participation in this protocol.

If the RA, AxSpA or IIM subject has had prior NIH laboratory and clinical examinations as part protocol #'s 01AR0227 Natural History of Rheumatic Disease in Minority Communities, 00AR0222 Natural History of Arthritis and Related Conditions, and 11AR0223 Studies on the Natural History and Pathogenesis of Spondylarthritis, those results may be used to better understand the subject’s current condition. Finally, results within the past year from these three natural history protocols can be used as part of screening, rather than repeat these tests under this protocol.

For Phase 4 patients, in addition to a basic rheumatology exam, we will do a Health Assessment Questionnaire Disability Index ([HAQ-DI for rheumatoid arthritis](#)) and the Disease Activity Score in 28 joints (DASB28). The DAS28 is a disease activity score (Prevoo *et al.*, 1995). These assessments will be done before both scans of Phase 4.

Healthy volunteers will be screened under protocol 01M0254 or 17M0181. Basic screening may include physical exam, medical history, and laboratory tests: CBC; acute care

panel; urine pregnancy test (females); HIV screening test; and EKG. Screening results will be reviewed by a clinically credentialed investigator before the subject undergoes any specific study procedures.

Consent will be obtained before any study procedures, including screening procedures done under this protocol.

d. Study procedures

1) PET Procedures

i. Radioligands

[¹¹C]MC1 will be prepared according to the IND and administered via an indwelling intravenous catheter over approximately one to three minutes.

ii. Insertion of the intravenous and/or arterial line

Two intravenous lines may be placed in the arms. They are used for the injection of radioligand and for drawing venous blood to measure the plasma radioactivity level in each time point during the scan. The lines are removed at the end of the day. For Phase 3, an arterial catheter will be inserted in the radial artery.

iii. PET scan

For whole-body scans (Phase 2 and 4), PET imaging will be performed using PET/CT scanner for about two hours for RA, IIM patients and healthy volunteers. AxSpA patients will undergo imaging using PET/MRI scanner for about two hours. Participants will be placed on the scanner bed, and to minimize extraneous motion, they may wear a head-holding mask and have their arms and abdomen wrapped with body-restraining sheets. Almost all subjects find this restraint comforting (i.e., they are not afraid of falling off the table), and none have found it intolerable. Pre-injection CT transmission scan (for PET) will be performed to measure and correct for attenuation. After an intravenous bolus of up to 15 mCi, several venous blood samples may be drawn from the venous catheter at discrete time points during the PET scan. The total amount of sampling volume will be up to 50 mL in each scan. PET image will be acquired in three-dimensional mode with increased length of frame for a total of approximately two hours. After the scan, the venous line will be removed, and the subject will be instructed to void frequently to minimize radiation exposure.

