2. STUDY OBJECTIVES

a. Primary objectives

- To evaluate the PET radioligand [¹¹C]MC1 as a new inflammatory biomarker in representative disorders with active inflammation: RA, AxSpA and IIM, compared to healthy condition.

- To evaluate the specific binding of [¹¹C]MC1 to COX-2 at the inflammatory focus in patients versus the same body part in healthy subjects through blocking study using a selective COX-2 inhibitor.
- To measure the brain uptake of [¹¹C]MC1 in brain of RA patients, in comparison to healthy volunteers.
- To evaluate the change of [¹¹C]MC1 binding to COX-2 at the inflammatory focus in RA patients: while having moderate to severe symptoms and after two to four months of clinically indicated treatment.

b. Secondary objectives

- To collect the human biodistribution and dosimetry data of [¹¹C]MC1.
- To see if the uptake of [¹¹C]MC1 at the inflammatory focus is correlated with the patient's available clinical profiles: clinical severity, serum biomarkers, X-ray or MRI findings, synovial/muscle biopsy findings, etc.
- To see if the uptake of [¹¹C]MC1 at the inflammatory focus is correlated with the patient's clinical rating scales and laboratory tests.

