9. OUTCOME MEASURES

a. Primary outcome measures

- Phase 2: Difference of [¹¹C]MC1 binding between patients and healthy subjects, and between inflamed and uninflamed body parts in RA patients.
- Phase 2: The specificity of [¹¹C]MC1 binding to COX-2 evaluated by celecoxib-blocking study.
- Phase 3: Quantitative measure of enzyme density (V_T) at baseline and after celecoxib blockade in patients compared to healthy controls.
- Phase 4: The change of [¹¹C]MC1 binding to COX-2 after two to four months of clinically-indicated therapy.

b. Secondary outcome measures

- Biodistribution and dosimetry of [¹¹C]MC1.
- Clinical correlation of [¹¹C]MC1 inRA, AxSpA and IIM patients based on their clinical or laboratory parameters.

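### In Phase 2 every AxSpA patient is scanned on PET/MRI and every healthy control on PET/CT, with no bridging described, so the baseline AxSpA-versus-healthy uptake comparison cannot separate disease from scanner.

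*Combined protocol and SAP*

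**What the plan says.** Scanner allocation is the same wherever the protocol gives it (Précis II and III, Sections 4.a and 4.d.1.iii). Section 4.d.1.iii: "PET imaging will be performed using PET/CT scanner for about two hours for RA, IIM patients and healthy volunteers". Section 4.a: "Fifteen patients with RA, fifteen patients with IIM, and fifteen healthy volunteers will have two whole-body PET/CT scans"; "Fifteen patients with AxSpA will undergo two whole-body PET/MRI scans". The visit schedule in 4.a replaces PET/CT by PET/MRI for AxSpA, and notes that "MRI imaging will be done simultaneously with the PET scan". No group is split across scanners and nobody is imaged on both.

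The first primary objective (Section 2.a) evaluates the radioligand in "RA, AxSpA and IIM, compared to healthy condition". The second concerns "the inflammatory focus in patients versus the same body part in healthy subjects through blocking study". Section 9.a lists, for Phase 2, the difference in "binding between patients and healthy subjects", then the inflamed-versus-uninflamed contrast for RA only, and separately the celecoxib-blocking result. Précis IV says that both baseline uptake and percentage blockade are compared between patients and healthy subjects, and lists the inflamed-versus-non-inflamed contrast for RA, AxSpA and IIM.

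Section 10.a defines the measure as regional SUV, expresses post-celecoxib uptake as a percentage of baseline, and allows one adjustment, for venous blood radioligand level. Section 10.b calls Phase 2 exploratory, aims for at least 10 and at most 15 per group, and gives no effect size, SD, test or alpha.

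On attenuation, Section 4.d.1.iii describes a CT transmission scan with no exception for AxSpA, while Section 7.c says that PET/MRI involves no CT.

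**The concern.** SUV corrects for injected activity and body weight, not for the scanner that produced the image. When one group is wholly on one scanner and its comparator wholly on another, any systematic difference between scanners enters the group difference in full. A larger sample makes the combined quantity more precise but cannot split it, and no regression model can either.

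The AxSpA-versus-healthy comparison serves an objective that names AxSpA. If the observed SUV difference, or the lack of one, is of the same order as a plausible scanner offset, it could not be credited to disease. An offset in the direction of disease could look like a signal, and one against it could hide a real signal. The venous-blood adjustment deals with delivery of the radioligand and does not address scanner response.

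**Working it through.** **1. Head count.** Four Phase 2 groups of 15 plus two Phase 1 subjects: 4 × 15 + 2 = 62, as in Section 10.b. This is an accrual figure with no power calculation behind it.

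**2. Estimability.** Build the Phase 2 design matrix from the allocation in Section 4.a: 60 rows and columns for intercept, RA, IIM, AxSpA and scanner (1 = PET/MRI). The AxSpA and scanner columns are identical (correlation 1.0), so the rank is 4 with 5 columns. The AxSpA effect alone is not estimable; only AxSpA + scanner is. This step needs no assumption. The RA and IIM contrasts with healthy are estimable because all three groups are on PET/CT.

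**3. How much an offset could matter.** The documents give no offset and no SUV variability, so the rest is illustration. Assume log-scale SD 0.20 or 0.30, n = 15 per group, a two-sample t test at two-sided 0.05 as a yardstick, and no disease effect. The noncentrality is ln(1 + b) / (SD × √(2/15)), with 28 degrees of freedom, where b is the assumed proportional offset.

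| Offset b | Noncentrality, SD 0.20 / 0.30 | P(nominal p<0.05), SD 0.20 / 0.30 |
|---|---|---|
| 2% | 0.27 / 0.18 | 5.8% / 5.4% |
| 5% | 0.67 / 0.45 | 9.9% / 7.1% |
| 10% | 1.31 / 0.87 | 24.3% / 13.4% |
| 20% | 2.50 / 1.66 | 67.4% / 36.2% |

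**4. Offset opposing a real difference.** Same method, with true ratio × (1 + b), where b is now negative. The +30% is an assumption. The +60% is the uptake increase that Section 1 reports for monkey brain after LPS, so it is indicative only.

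| b | Power at +30%, SD 0.20 / 0.30 | Power at +60%, SD 0.20 / 0.30 |
|---|---|---|
| 0 | 93% / 64% | 100% / 99% |
| -5% | 80% / 46% | 100% / 96% |
| -10% | 55% / 28% | 100% / 90% |
| -20% | 8% / 6% | 90% / 59% |

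**5. When a raw difference would still be informative.** For the lower 95% limit to exceed an assumed offset, the observed ratio must exceed (1 + b) × exp(t × SD × √(2/n)). With n = 15 (t = 2.048), the threshold is 1.22-1.31 for a 5% offset, 1.28-1.38 for 10% and 1.39-1.50 for 20%. At the minimum n = 10 (t = 2.101), it is 1.27-1.39, 1.33-1.46 and 1.45-1.59.

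**6. Percentage of baseline.** Let r be the true residual fraction and suppose the same scanner bias acts on both scans of a patient.
- A multiplicative factor k gives kr / k = r, so it cancels.
- An additive bias c (as a fraction of baseline) gives (r + c) / (1 + c). With no true blockade (r = 1) this is 1 for every c, so such a bias cannot create blockade.
- With an assumed r = 0.70, c = -0.20 gives 0.50 / 0.80 = 62.5% and c = +0.20 gives 0.90 / 1.20 = 75%. The size of blockade is therefore less protected than its presence.

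**The case against.** The strongest reply is that no harm is shown. The documents give no offset, and a protocol's silence on calibration does not mean that none is done; it may sit in site procedures. The study is exploratory and names no test, so rejection rates describe an analysis that the plan does not state. At small offsets the effect is slight, and a +60% difference would largely survive a 10% opposing offset. All of this stands, and it makes the harm conditional. It does not remove the aliasing, which follows from the allocation alone, and the exploratory label explains the missing power calculation but does not make an aliased contrast interpretable.

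A second reply is that raw SUV is not plainly a primary measure. Section 9.a speaks of binding, Section 4.a says specific binding can be estimated only by comparing baseline and blocked scans, and the second primary objective works through blocking. That is fair. But Section 9.a lists blockade as a separate item and Précis IV names baseline uptake as a comparison, so the raw contrast is the natural, though not explicit, reading of the first item.

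A reader might also infer more than the documents support:
- That all Phase 2 patient-versus-healthy comparisons are compromised. They are not: RA and IIM share PET/CT with controls.
- That the blocking result in AxSpA is invalid. Both AxSpA scans are on PET/MRI, and a multiplicative factor cancels.
- That the AxSpA comparison is biased or the scanners uncalibrated. The documents show neither.
- That controls must be rescanned. A documented cross-calibration could also deal with the problem.

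**Conclusion.** The point holds for one contrast. Disease and scanner are completely aliased in the baseline AxSpA-versus-healthy uptake comparison, and nothing in the analysis section separates them. That is certain from the documents. The consequence is not: it depends on an offset whose existence, size and direction are unknown. On the stated assumptions it ranges from negligible at 2% to serious at 20%, and a difference well above any plausible offset would remain informative. This should be fixed because the comparison serves a primary objective and the remedy is text. The mismatch between Sections 4.d.1.iii and 7.c on CT is a smaller matter of clarification, but it leaves an input to SUV unstated for the AxSpA scans.

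**What to change.** Amend Sections 4.d, 9.a and 10.a; no extra scans are needed.

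1. Base AxSpA conclusions on same-scanner contrasts: the percentage of baseline after celecoxib, already specified, and the inflamed-versus-non-inflamed contrast. Précis IV lists the latter for AxSpA but Section 9.a limits it to RA, so reconcile the two. Define inflamed regions from the simultaneous MRI before the PET is read, and use this contrast only in patients who have such a region. Appendix 1 allows entry through HLA-B27 plus other features without imaging sacroiliitis, so some may not. Note that ratios between regions do not remove attenuation error that differs by region.
2. Report the raw AxSpA-versus-healthy SUV difference as descriptive and confounded with scanner, unless a documented cross-calibration between the two scanners supports it.
3. For AxSpA versus healthy, prefer percentage blockade, with three stated caveats: only a multiplicative scanner factor cancels; the baseline scan always comes first (Section 4.a); and celecoxib may act peripherally, as Section 1 itself warns.
4. State how attenuation is corrected on PET/MRI, so that Sections 4.d.1.iii and 7.c agree.

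The cost is that the raw AxSpA contrast carries less weight and its confounding is disclosed, not removed. Removing it would take a documented cross-calibration, or controls imaged on PET/MRI or on both scanners. Imaging controls would add MRI screening, plus either extra scans or some loss of precision. These routes are optional and not needed for this fix.
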